When inflated, the cuff constricts the urethra and blocks the passage of any urine. When deflated, the cuff reduces pressure on the urethra and allows for the free passage of urine.

[figure not shown]

Figure 5 AUS with Foley catheter

A foley catheter is also inserted during surgery, which is removed prior to discharge from the hospital. The artificial sphincter cuff is not inflated immediately after surgery, in order to allow the tissues to heal.

Significance:

Post-prostatectomy urinary incontinence is a troubling complication following treatment (radical prostatectomy, radiation therapy, or brachytherapy) for prostate cancer, or in rare instances the treatment of benign prostatic hypertrophy, and significantly decreases quality of life in affected patients. An artificial urinary sphincter has been found to significantly improve quality of life in these patients. Providing data which demonstrates the safety and feasibility to activate an artificial urinary sphincter 3 weeks after surgery as opposed to 4-6 weeks will allow men to regain their continence earlier, therefore improve their quality of life.

Methods

Study Design:

The design will be a single institute prospective study with patients undergoing artificial urinary sphincter placement by the operating surgeon, [name] at Charleston Area Medical Center in Charleston, WV. All patients following informed consent that meet the inclusion criteria are eligible to participate in the study.

Sample:

All male patients with moderate to severe urinary incontinence who have been treated for prostate cancer (radical prostatectomy, External Beam Radiation therapy or brachytherapy, or Incontinence related to trans urethral resection of the prostate (TURP) or simple prostatectomy undergoing artificial urinary sphincter placement at Charleston Area Medical Center by [name], D.O. will be offered the chance to participate in this study. This is a pilot study and thus no power analysis to calculate necessary sample size is conducted to determine a number that would yield sufficient power. We will aim to enroll 25 patients, which we anticipate to be accrued within 3 years from the start of the study. We will have 1 study group: those who are activated at 3 weeks post implantation.

Inclusion Criteria:

All patients undergoing artificial urinary sphincter (AUS) placement by a single surgeon, [name].

Exclusion Criteria:

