- History of medication
- Date device is activated
- Comorbidities
- ECOG Score

- ASA Score
- Tobacco Use
- Diabetes

When the study patient follows up at 3 weeks postoperatively, we will assess for immediate postoperative complications:

- Post-operative urinary retention Y/N
- Bleeding Y/N
- Presence/concern for infection Y/N
- Presence/concern for urethral erosion Y/N

When any patient follows up at 6 weeks, 6 months, and 12 months postoperatively, we will assess:

- Postoperative daily pad usage
- Perceived improvement in incontinence (scale 1 (none) 10 (very satisfied))
- Presence/concern for infection Y/N
- Presence/concern for urethral erosion Y/N
- Post-surgery SF-8 surveys (6 weeks, 3 months, 6 months)

Statistical Analysis:

The Center of Health Service and Outcomes Research will conduct the data analysis. For this exploratory study, selection of appropriate statistical measure will be determined by CAMC Center for Health Education and Research Institute. Specific tests will be determined by whether the data is continuous or categorical. Descriptive statistics will be used as appropriate and comparisons will be done using student's T-test and chi-square test. In addition univariate and multivariate multiple logistic regressions will be used to determine which variables predict patient's outcomes. All comparisons will be done at 95% of level of significance.

I. Human Subjects

Study population: All patients undergoing artificial urinary sphincter (AUS) placement by a single surgeon, [name] at Charleston Area Medical Center.

Recruitment methods: All patients, following informed consent, that meet the inclusion criteria are eligible to participate in the study. Patients will be consented by the principal investigator only at time of usual surgical informed consent using the attached consent form. Consent will be obtained prior to the surgical procedure.

Benefits: Early activation of the artificial urinary sphincter will allow the patient to regain continence earlier.

Risks and discomforts: The principle risks of participation in this study will be the standard risks of the operation.

Less often, there are risks of bleeding, infection, urinary tract injury, device erosion, wasting away of muscle mass in the urinary tract, or loss of bladder control.

Occasionally, there are risks of persistent loss of bladder control or mechanical failure of device.

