	o while remange affected your.	Not at All	Slightly	Moderately	Greatly		
1.	Ability to do household chores (cooking, housecleaning, laundry)?	0	1	2	3		
2.	Physical recreation such as walking, swimming, or other exercise?	0	1	2	3		
3.	Entertainment activities (movies, concerts, etc.)?	0	1	2	3		
4.	Ability to travel by car or bus more than 30 minutes from home?	0	1	2	3		
5.	Participation in social activities outside your home?	0	1	2	3		
6.	Emotional health (nervousness, depression, etc.)?	0	1	2	3		
7.	Feeling frustrated?	0	1	2	3		
	ms 1 and 2 = physical activity m 5 = social/relationships	Items 3 and 4 = travel Items 6 and 7 = emotional health					

Scoring. Item responses are assigned values of 0 for "not at all," 1 for "slightly," 2 for "moderately," and 3 for "greatly." The average score of items responded to is calculated. The average, which ranges from 0 to 3, is multiplied by 33 1/3 to put scores on a scale of 0 to 100.

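### Logistic is the only regression named for finding predictors, yet four outcomes are numeric or ordinal and have neither a named model nor a cut-point

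*Combined protocol and SAP*

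**What the plan says.** The Statistical Analysis section contains four statements that bear on this point.

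- Method choice is left open: "selection of appropriate statistical measure will be determined by CAMC Center for Health Education and Research Institute".
- Tests follow the type of data: "Specific tests will be determined by whether the data is continuous or categorical".
- Two tests are named: "comparisons will be done using student's T-test and chi-square test".
- One regression is named: "In addition univariate and multivariate multiple logistic regressions will be used to determine which variables predict patient's outcomes".

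The section does not say which outcomes the regression covers. It names no linear, ordinal or count model and gives no cut-point.

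The outcomes are listed elsewhere. Data Collection and Management includes "Postoperative daily pad usage", a rating described as "Perceived improvement in incontinence (scale 1 (none) 10 (very satisfied", and the SF-8. The Study Chart adds the IIQ-7, whose scoring in Appendix A reads: "The average, which ranges from 0 to 3, is multiplied by 33 1/3 to put scores on a scale of 0 to 100". Retention, bleeding, infection and erosion are recorded as yes or no.

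On size, the Sample section says: "We will aim to enroll 25 patients, which we anticipate to be accrued within 3 years from the start of the study". It also says that no power analysis was done.

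**The concern.** Binary logistic regression needs a yes/no outcome. The IIQ-7 has 22 possible values when all seven items are answered (total 0 to 21). Pads are a count, the improvement rating has ten levels, and the SF-8 is built from eight graded items. To put any of these into a binary logistic model, someone must choose a threshold. Every man on the same side of it is then treated as having the same result.

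The named tests do not fill the gap. Several recorded predictors are themselves numeric: age, BMI, operative time and preoperative pads. For a numeric predictor and a numeric outcome, a t-test needs two groups, chi-square needs two categorical variables, and binary logistic regression needs a yes/no outcome. Unless a method outside the named list is used, one of the two variables has to be cut.

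Two things are at stake. With about 25 men, there is little information to spare on which characteristics go with better continence and quality of life. And with no cut-point or alternative model in the plan, nothing prevents that choice from being made after the data are seen.

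**Working it through.** **What the plan gives.** The sample size is 25 in one group. The 95% level in Statistical Analysis is read here as a 5% test; two-sided is an assumption. There is no stated power, effect size or predictor–outcome correlation, so there is no figure of the plan's own to reproduce.

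**Counting the outcomes.** From 6 weeks on, six distinct outcomes are collected: four numeric or ordinal (pads, rating, SF-8, IIQ-7) and two yes/no (infection, erosion). Adding retention and bleeding from the 3-week visit makes it four and four.

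**Assumptions for the size.** One continuous predictor, bivariate normal with the outcome; correlation r from 0.2 to 0.6; outcome cut at the median or 80/20. For context, the Background cites success of 60% to 90% under a 0–1 pad definition. If that were the cut, splits would run from 60/40 to 90/10.

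**Tests compared at n = 25.**

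- Full scale: t = r̂√(n−2)/√(1−r̂²), where r̂ is the sample correlation, compared with the t distribution on 23 degrees of freedom.
- After the cut: single-predictor logistic regression, likelihood-ratio statistic 2(ℓ₁−ℓ₀) compared with 3.84.

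**Simulated power, 20,000 runs per cell** (full scale → cut; losses in percentage points, taken from unrounded values):

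| r | Median cut | Loss | 80/20 cut | Loss |
|---|---|---|---|---|
| 0.2 | 16.0% → 14.1% | 1.9 | 16.2% → 12.9% | 3.2 |
| 0.3 | 30.7% → 24.2% | 6.5 | 31.3% → 20.3% | 11.0 |
| 0.4 | 52.4% → 38.7% | 13.7 | 52.6% → 32.2% | 20.4 |
| 0.5 | 75.4% → 57.5% | 17.9 | 75.1% → 46.0% | 29.0 |
| 0.6 | 91.1% → 76.4% | 14.8 | 91.1% → 62.8% | 28.3 |

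A separate simulation gave 51% against 39% at r = 0.4 with a median cut, a loss of 12. Allowing for such differences between runs, the ranges are about 1–3 points at r = 0.2, 7–11 at r = 0.3 and 12–29 at r = 0.4 to 0.6.

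**Analytic check.** Cutting at quantile q shrinks the correlation to r* = r·φ(z_q)/√(q(1−q)), and power ≈ Φ(atanh(r*)·√(n−3) − 1.96). For r = 0.5:

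- Full scale: atanh(0.5)·√22 = 0.549 × 4.690 = 2.576, so power is Φ(0.616) = 73%.
- Median cut: r* = 0.5 × 0.798 = 0.399; 0.422 × 4.690 = 1.981; Φ(0.021) = 51%.
- 80/20 cut: r* = 0.5 × 0.700 = 0.350; 0.365 × 4.690 = 1.714; Φ(−0.246) = 40%.

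The approximation gives somewhat larger losses (22 and 33 points) than the simulation, in the same direction.

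**Sensitivity.**

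- *90/10 cut, likelihood-ratio test:* the loss runs from 4 points (r = 0.2) to 44 (r = 0.6).
- *Wald test:* the loss is larger. At r = 0.5, power is 44% with a median cut and 24% with an 80/20 cut.
- *Two-level predictor, 12.5 men per level, median cut:* comparing means at standardised difference d with comparing proportions Φ(−d/2) and Φ(d/2), the loss is 8, 18, 23, 22 and 14 points for d = 0.5, 0.8, 1.0, 1.2 and 1.5.
- *Floored pad counts* (60% or 79% of men assumed at 0–1 pads, cut there): the loss was about −1 to +1 point at r = 0.2, 2–4 at r = 0.3 and 4–14 at r = 0.4 to 0.5. These figures depend on the assumed shape of the counts and move towards the normal-score losses as the counts become less skewed.

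**The case against.** The strongest reply is that the plan does not require any score to be cut. It says tests will follow data type, leaves the choice of method to the institute, and does not list the outcomes for the regression. An ordinal logistic model would need no binary split. This stands: a reader might infer that every numeric outcome must be reduced to yes/no, and the documents do not support that. What they show is narrower. No model is named for these outcomes, and the one regression that is named would, in its binary form, need a cut that is not defined.

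A reader might also infer that most outcomes do not suit logistic regression. That is true of the visits from 6 weeks on, but over all distinct post-operative outcomes the split is even. The yes/no items carry the safety aim, and logistic regression suits them in type.

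A third tempting reading is a fixed power loss of 14 to 29 points. That needs correlations of roughly 0.4 to 0.6, cuts between the median and 80/20, a near-normal score and the likelihood-ratio test. The documents give none of these. At r = 0.2 almost nothing is lost, because full-scale power is itself only 16%. Bivariate normality also favours linear regression.

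Nor should the error rate be counted against the plan here. With no true association, the likelihood-ratio test rejected about 6.4% of the time and the Wald test 2% to 3%, against 5% for linear regression. That is a small-sample problem, and it would remain for the complications whichever model is used for the scores.

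Finally, the study is an exploratory pilot without a power analysis, and the regression is an additional analysis. This lowers the priority but does not remove the gap. Improved patient satisfaction is part of the stated hypothesis, and the numeric scales are where it would show.

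**Conclusion.** The point holds as an omission that is cheap to repair. The only regression named for finding predictors is logistic, four outcomes are numeric or ordinal, and the plan gives neither a model nor a cut-point for them. A binary cut would discard information; for roughly normal scores, power fell in every setting examined with a true association. The size is conditional: about 1–3 points at r = 0.2, 7–11 at 0.3 and 12–29 at 0.4–0.6, assuming n = 25, one normal predictor, a normal outcome, a two-sided 5% level, the likelihood-ratio test and cuts from the median to about 80/20. It is smaller for heavily floored pad counts. Priority is low to moderate, because no stated decision depends on this analysis.

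**What to change.** In Statistical Analysis, replace the regression sentence with text to this effect:

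- Predictors of the IIQ-7, SF-8, daily pads and perceived improvement will be examined on the full scale. Linear regression will be used for scores, adjusted for the pre-operative value where one is collected (IIQ-7, SF-8, pads). Ordinal, count or rank-based methods will be used for pads and the 1–10 rating.
- Logistic regression will be used for outcomes that are yes/no by nature, that is, the complications.
- Any cut-point, such as 0–1 pad per day for comparison with the literature, will be stated before the data are examined.

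The cost is wording only: no new data, visits or patients. The downside is that results for these outcomes will be slopes or mean differences rather than odds ratios, and skewed scores will need a check with a rank-based or ordinal method.

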Appendix A:

			Artific	ial Urin	ary Sphi	ncter		
	Directions Shade circles like Do not shade like		SF-	8 Health	Survey	Please complete using blue or black ink.		
	t Name:				Pa	tient study numbe		
O 6	re-op Visit Week Follow-up Month Follow-up Month Follow-up	Visit	Date o	if Completion of S	urvey: /	1		
1.	Overall, how wo	ould you rate you	ur health during t	he past 4 weeks?				
	O Excellent	O Very Go	ood O Good	O Fair	O Poor O Very	/ Poor		
2.	During the past 4 weeks, how much did physical health problems limit your usual physical activities (such as walking or climbing stairs)?							
	O Not At All	O Very Little	O Somewhat	O Quite A Lot	O Could Not Do	Physical Activities		
3.	During the past 4 weeks, how much difficulty did you have doing your daily work, both at home and away from home, because of your physical health?							
	O Not At All	O Very Little	O Somewhat	O Quite A Lot	O Could Not Do	Physical Activities		
4.	How much bodil	y pain have you	had during the	oast 4 weeks?				
	O Not At All	O Very Little	O Somewhat	O Quite A Lot	O Could Not Do	Physical Activities		
5.	During the past 4 weeks, how much energy did you have?							
	O Not At All	O Very Little	O Somewhat	O Quite A Lot	O Could Not Do	Physical Activities		
6.	During the past 4 weeks, how much did your physical health or emotional problems limit your usual social activities with family or friends?							
	O Not At All	O Very Little	O Somewhat	O Quite A Lot	O Could Not Do	Physical Activities		
7.	During the past 4 weeks, how much have you been bothered by emotional problems (such as feeling anxious, depressed or irritable)?							
	O Not At All	O Very Little	O Somewhat	O Quite A Lot	O Could Not Do	Physical Activities		
8.	During the past 4 weeks, how much did personal or emotional problems keep you from doing your usual work, school or other daily activities?							
	O Not At All	O Very Little	O Somewhat	O Quite A Lot	O Could Not Do	Physical Activities		
		THANK Y	OU FOR COMP	LETING THIS Q	JESTIONNAIRE!	Draft		

Version 2: 03/11/2019 Page 13

Incontinence Impact Questionnaire – Short Form IIQ-7

Some people find that accidental urine loss may affect their activities, relationships, and feelings. The questions below refer to areas in your life that may have been influenced or changed by your problem. For each question, circle the response that best describes how much your activities, relationships, and feelings are being affected by urine leakage.

Has urine leakage affected your:

	o while remange affected your.	Not at All	Slightly	Moderately	Greatly		
1.	Ability to do household chores (cooking, housecleaning, laundry)?	0	1	2	3		
2.	Physical recreation such as walking, swimming, or other exercise?	0	1	2	3		
3.	Entertainment activities (movies, concerts, etc.)?	0	1	2	3		
4.	Ability to travel by car or bus more than 30 minutes from home?	0	1	2	3		
5.	Participation in social activities outside your home?	0	1	2	3		
6.	Emotional health (nervousness, depression, etc.)?	0	1	2	3		
7.	Feeling frustrated?	0	1	2	3		
	ms 1 and 2 = physical activity m 5 = social/relationships	Items 3 and 4 = travel Items 6 and 7 = emotional health					

Scoring. Item responses are assigned values of 0 for "not at all," 1 for "slightly," 2 for "moderately," and 3 for "greatly." The average score of items responded to is calculated. The average, which ranges from 0 to 3, is multiplied by 33 1/3 to put scores on a scale of 0 to 100.

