Any patient who has previously undergone artificial urinary sphincter placement and presents for revision or additional cuff placement.

Any patient who is undergoing combined artificial urinary sphincter and inflatable penile prosthesis placement.

Any patient who is a poor candidate for early activation due to poor condition at presentation or signs of infection.

Procedures and Protocol:

There isn't a comparison group for this study; therefore all patients agreeing to participate will have the urinary sphincter activated 3 weeks after surgery. If there are patients that later choose not to have early activation or are found to be poor candidates for three week activation based upon their post op

exam, we will proceed with activation at a 4-6 week time period. While there is no comparison group in the study, patient satisfaction and adverse events for study patients will be compared to historical literature.

Currently patients are not routinely seen for a 3 week follow up appointment, so approximately \$3000 will be requested from Research appropriations to cover the costs of this study. All other costs are standard of care, so patient will be responsible for those costs whether they agree to enroll in the study or not. The money from the CAMC Research Appropriations will be used to cover all the clinical fees for the 3 week visit to activate the AUS.

Pre-procedure:

- 1. All eligible patients will be informed about the study at their regularly scheduled pre-operative office visit. If the patient agrees to participate, they will be consented with the consent form as written. A note is made in the progress note of the patient's chart detailing the consent.
- Original signed consent will be kept and stored in the consent binder at [name] office and one copy of the consent will be placed in the medical record and another will be given to the participant.
- 3. Patient will complete an SF-8 quality of life survey and Incontinence Impact Questionnaire (Appendix A).

Intraoperative procedures:

1. Once consented, the patient will undergo the procedure without any changes to our normal routine. The patient's device will be deactivated at the conclusion of the procedure.

Post-procedure:

- 1. The patient will be discharged post-operatively (same day) and follow-up will be arranged in 3 weeks to activate the device.

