- 2. Study patients have a follow up office visit at 3 weeks (up to 3 weeks and 3 days after the procedure) which includes a post-operative evaluation of their incisions, degree of bruising, tissue induration, tenderness and accessibility of the pump. If these factors are acceptable and pump mechanics are normal, the artificial sphincter will be activated and the patient will be educated on its proper use.
- 3. Additional follow up will include the regular 6 week visit, a visit at 3 months, and then every 6 months for a total of 1 year unless issues arise that necessitates deviation. At each visit, patients will complete the Incontinence Impact Questionnaire and the SF-8 quality of life survey.

Study Chart:

INFORMATION	PRE-	Intra-	POST-Treatment	POST-	POST-	POST-	POST-Operative
	Treat	operative	3 weeks	OperativeTrea	Operative	Operative	Treatment 1 year
	ment	Treatment	(up to 3 weeks and	tment	Treatment 3	Treatment	(+ 1 month)
			3 days after	6 weeks	months	Six months	
			procedure)	(+ 1 week)	(+ 2 weeks)	(+ 3 weeks)	
Inform Subject	Х						
Consent Subject	Х						
Note in Record	Х						
Office visit	Х		Х	X	Х	Х	Х
SF-8 survey administered	Х			Х	Х	Х	Х
Incontinence Impact Questionnaire	Х		Х	Х	х	Х	Х
Procedure conducted		Х					
Data Collection	Х	X	Х	Х	Х	Х	Х

Data Collection and Management:

The SF-8 is a quality of life instrument related to health functioning that provides an eight question brief assessment of physical and mental health⁶. It has been found to have adequate reliability and validity in prior studies for quality of patient life and it incorporates a manual for easy interpretation.⁷. The Incontinence Impact Questionnaire short form was adapted from a survey that was developed for women with stress incontinence. This questionnaire has been validated for use in men after radical prostatectomies and consists of 7 items in which measures the effect of Urinary Incontinence on quality of life⁸.

Following surgery, patient characteristics and operative details will be recorded. These will include:

- Medical Record Number
- Patient name
- Age
- BMI
- Operative time
- Artificial sphincter cuff size
- Pressure-regulating balloon size
- Intra-operative complications (urethral injury, bleeding)
- Reason for AUS placement (Post-prostatectomy, Radiation therapy for prostate cancer, or Incontinence related to TURP)
- Finish date of prostate cancer treatment or TURP
- Preoperative daily pad usage
- Pre-surgery SF-8 survey

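### As extracted, the SF-8 page in Appendix A ends items 4 to 8 with an option that does not answer them; separately, the protocol gives conflicting SF-8 and IIQ-7 schedules

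*Combined protocol and SAP*

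**What the plan says.** **The form.** Under Pre-procedure, item 3 reads "Patient will complete an SF-8 quality of life survey and Incontinence Impact Questionnaire (Appendix A", so the Appendix A pages are the study instruments. On the SF-8 page, item 1 has its own row of six answers. Items 2 to 8 share a row of five, and the fifth is "O Could Not Do Physical Activities" (the leading O is the answer circle). One of these items is "During the past 4 weeks, how much energy did you have".

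**The schedule.** Four places bear on when the questionnaires are given.

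- Post-procedure, item 3, lists a 6-week visit, a 3-month visit, "and then every 6 months for a total of 1 year", and adds: "At each visit, patients will complete the Incontinence Impact Questionnaire and the SF-8 quality of life survey".
- The Study Chart marks the SF-8 before treatment and at 6 weeks, 3 months, 6 months and 1 year. It marks the IIQ-7 at the same visits and also at 3 weeks.
- Data Collection and Management opens its follow-up list with "When any patient follows up at 6 weeks, 6 months, and 12 months postoperatively, we will assess", but the SF-8 entry in that list is "Post-surgery SF-8 surveys (6 weeks, 3 months, 6 months".
- The Intervention paragraph under Human Subjects places both questionnaires at the initial office visit, 6 weeks, 3 months and 6 months.

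**The concern.** There are two separate problems.

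First, an answer that does not fit its question leaves the patient to guess its meaning and the analyst to guess what the patient meant. The option concerns physical activity. Items 4 to 8 ask about pain, energy, social activities, emotional bother, and usual work, school or daily activities.

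Second, staff who work from the Intervention paragraph or from the SF-8 data line could close out a patient without the 1-year SF-8 that the chart requires. Those who work from the Intervention paragraph could also miss two IIQ-7 administrations. One of these is at 3 weeks, the activation visit, where the chart has no other questionnaire.

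The Significance section gives better quality of life as the reason to activate earlier, so these data matter to the case the study wants to make, even in a pilot.

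**Working it through.** No figure in the plan needs reproducing, and no power calculation is involved. The check compares the text item by item and visit by visit.

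**Step 1. The last SF-8 option against each item that carries it**

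| Item | Subject | Does the last option answer it? |
|---|---|---|
| 2 | Limits on physical activities | Yes |
| 3 | Difficulty with daily work | Loosely |
| 4 | Bodily pain | No; position suggests worst |
| 5 | Energy | No; position and wording conflict |
| 6 | Limits on social activities | No; position suggests worst |
| 7 | Emotional bother | No; position suggests worst |
| 8 | Work, school, daily activities | No; position suggests worst |

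The option fails to answer 5 of the 8 items, and loosely fits a sixth. On items 4 and 6 to 8 the answers run from none to a great deal of a problem, so the fifth place can still be taken as the worst level. On item 5 they run from no energy to a lot of energy. The fifth place would then be the most energy, yet the words describe incapacity. The first four options can be used on every item from 2 to 8.

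**Step 2. The schedules side by side**

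| Visit | SF-8, chart | SF-8, data line | SF-8, Intervention | IIQ-7, chart | IIQ-7, Intervention |
|---|---|---|---|---|---|
| Before surgery | yes | (post-surgery only) | yes | yes | yes |
| 3 weeks | no | no | no | yes | no |
| 6 weeks | yes | yes | yes | yes | yes |
| 3 months | yes | yes | yes | yes | yes |
| 6 months | yes | yes | yes | yes | yes |
| 1 year | yes | no | no | yes | no |
| Total | 5 | 3 | 4 | 6 | 4 |

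- Chart less Intervention paragraph: SF-8, 5 − 4 = 1 (1 year); IIQ-7, 6 − 4 = 2 (3 weeks, 1 year); 3 in all.
- Chart less data line, post-surgery SF-8: 4 − 3 = 1 (1 year).

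The data line also disagrees with the heading of its own list: it includes 3 months, which the heading omits, and leaves out 12 months, which the heading includes.

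**Step 3. The most that could be lost**

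The Sample section aims for 25 patients. With full attendance the chart yields 25 × (5 + 6) = 275 questionnaires and the Intervention paragraph 25 × (4 + 4) = 200. The difference is 75: 25 SF-8 at 1 year, 25 IIQ-7 at 3 weeks and 25 IIQ-7 at 1 year. This is an upper bound under the assumption that every site action follows the Intervention paragraph. It is not a forecast. The documents give no basis for estimating how many patients would choose the last SF-8 option.

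**The case against.** **On the form.** The Appendix A text was read by machine and is damaged in places, so the option row might be an artefact. Against that, the visible damage consists of lost or altered characters. The same clean wording appears under seven items, and item 1 keeps a different row. An artefact is unlikely but not excluded, so the original must be checked first.

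A reader might go further in four ways that the documents do not support.

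- Item 5 runs in the opposite direction to its neighbours. That is not a defect: questionnaires may contain such items, the protocol says the SF-8 comes with a manual, and nothing says item 5 will be coded like the rest.
- The page carries the word Draft. This may be a mark from form software and does not show that the form was unapproved.
- The visit labels read "re-op Visit Week Follow-up Month Follow-up Month Follow-up", which looks like four boxes for five charted SF-8 visits. But this line is badly damaged, a lost box cannot be ruled out, and the month numbers are missing. It is a reason to check the page, not evidence of a missing box.
- The page might be thought to depart from the licensed SF-8. That cannot be judged from these documents.

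It is also too strong to call every last-category answer on items 4 to 8 meaningless. Position still points to the worst level on items 4 and 6 to 8; only item 5 is truly ambiguous.

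**On the schedule.** The Post-procedure text and the chart are the detailed visit schedule and agree on 1 year for both instruments. The Intervention paragraph is a summary and does not say its list is exhaustive. That lowers the chance of missed forms but does not remove the conflict, because the SF-8 data line also stops at 6 months. The 3-week question is less clear. Only the chart places the IIQ-7 there, and the sentence about each visit follows a list that starts at 6 weeks. If that sentence were read to include 3 weeks, it would call for an SF-8 that the chart leaves out.

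**On importance.** This is a small pilot, and the Statistical Analysis section names no SF-8 or IIQ-7 endpoint. That limits the consequence; it does not make the passages agree.

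**Conclusion.** Both parts hold, and both should be corrected.

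The form defect is conditional: if the original page reads as extracted, the last option does not answer 5 of 8 SF-8 items, fits item 3 only loosely, and is contradictory on item 5. The schedule defect does not depend on the SF-8 page. Three charted questionnaire administrations are missing from the Intervention paragraph, and one of them, the 1-year SF-8, is also missing from the data line.

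A reader might infer that the study's safety findings are compromised. They are not: complications are recorded separately, and the effect is confined to quality-of-life data. Confidence is moderate, because the form part awaits sight of the original page.

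**What to change.** 1. Check the original Appendix A page. If it reads as extracted, replace it with a form whose options answer each item, scored by the SF-8 manual that the protocol cites.
2. Give one questionnaire schedule in the Post-procedure text, Study Chart, Data Collection and Management, and Intervention paragraph. Keep the 1-year assessment already in the Post-procedure text and chart. Decide and state whether each questionnaire is given at 3 weeks.
3. Check that the SF-8 form has a visit box for every scheduled SF-8 visit.
4. If forms have already been completed on this page, report the number of last-category answers on items 3 to 8 and treat those on item 5 as ambiguous. Analyse items 4 and 6 to 8 twice: once with the last category as the worst level and once with it set to missing. Setting it to missing alone could remove the most impaired answers and make quality of life look better than it was.

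The cost is a short amendment, with one page replaced if the check confirms the wording. Last-category answers on items 3 to 8 from the old and new forms should not be pooled without the sensitivity analysis in step 4.
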